## 2.5. Definition of Subgroups

The following demographic and screening/baseline characteristics will be used to define subgroups of interest for efficacy analyses (primary endpoint and key secondary endpoint) and selected safety analyses (see Section 6).

### 2.5.1. Subgroups for Efficacy Analyses

- Age categories: 18 years -≤30 years, >30 years
- Race: Asian, non-Asian
- ALT level at baseline: normal, >ULN
- HBsAg level at baseline:
  - <10,000 IU/mL
  - ≥10,000 IU/mL-<100,000 IU/mL
  - ≥100,000 IU/mL
- HBV DNA level at screening:
  - <10^7 IU/mL
  - ≥10^7 IU/mL
- Immune tolerant at baseline
  - Yes: HBV DNA level > 7 log10 IU/mL and ALT ≤ULN
  - No: HBV DNA level ≤ 7 log10 IU/mL or ALT >ULN
- Pegylated Interferon responder definition #1
  - First, compare the ALT maximum value between Consolidation Baseline and FU Week 4 with the last value of ALT before or at the first Pegylated Interferon intake date. If the increase in ALT is >=100%, then the patient is considered as a “responder” to Pegylated Interferon. If the increase in ALT is <100%, then the patient is considered as a “non-responder” to Pegylated Interferon. Only patients who have received at least one dose of Pegylated interferon are considered.
- Pegylated Interferon responder definition #2

A linear regression model using the four last HBsAg measures before Consolidation Baseline is performed to estimate predicted value of HBsAg at CW12. If a decline higher than 0.5 log10 HBsAg is observed compared to the predicted value, then the patient is considered as a “responder” to Pegylated Interferon. Only patients who have received at least one dose of Pegylated interferon are considered.

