### Amendment 4:

Overall rationale of this Amendment:

This administrative amendment incorporates additional clarifications on subgroups and analyses which have been documented in the Data Presentation Specification.

Clarifications, Additions, Corrections		
Section Number and Name	Description of Change	Rationale
2.5.1 Subgroup for Efficacy Analyses	
Addition of the following subgroups:
 
 
- Immune tolerant
 
- Peg-responder definition #1
 
- Peg-responder definition #2
 
 
Removal of the following subgroups:
 
 
- NA treatment history
 
- Fibrosis stage
 
- Sex
 
- Geographical region
 
- Duration of exposure to antigens
 
 
Regrouping of the age categories: >30 years - ≤45 years, >45 years - ≤55 years in one category: >30 years
	To allow for a more focused assessment of factors impacting efficacy outcomes and reduce the overall number of outputs
5.4.1.3.1. Association Between Baseline Characteristics/Viral Blood Markers and Selected Efficacy Variables	Removal of the correlation analyses between off-treatment HBV markers and other endpoints	Insufficient data for correlation analysis since there is only one patient who has met the NA treatment completion criteria and stopped NA (i.e. off-treatment) at CW12.
5.4.1.3.1. Association between several endpoints	The title has been changed to reflect the analyses detailed in this subsection.	To characterize association between changes in viral and safety markers during PegIFN administration.

Clarifications, Additions, Corrections		
Section Number and Name	Description of Change	Rationale

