### 5.1.2. Data Handling Rules

Those measurements collected from screening visit to the end of study will be handled according to the following rules summarized in Table 4.

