### **5.2.3. Subgroup Analyses of Primary Efficacy Endpoint**

The primary efficacy endpoint will be summarized descriptively using the number and percentage of participants by cohort by each subgroup of interest (Section 2.5.1).

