### **5.3.1.1.3. HBsAg Sero clearance**

Sero clearance of HBsAg is defined as a (quantitative) HBsAg level <LLOQ. HBsAg sero clearance may be achieved prior to the time point assessed but must be observed at the given week of interest.

HBsAg sero clearance will be evaluated over all time points when assessed.

HBsAg sero clearance will be also evaluated when assessed at all time points after stopping all study interventions (regardless when intervention was stopped) and without restarting NA treatment.

If the HBsAg value at FU Week 12 is missing, the next available observation will be used. The next non-missing lab test no later than FU Week 24 will be imputed.

If the HBsAg value at FU Week 24 is missing, the LOCF in conjunction with the next available observation imputation approach will be used. The available non-missing lab test closest to FU Week 24 which is no earlier/later than 12 weeks from the actual time point of interest (FU Week 12 and FU Week 36, respectively) will be imputed.

If the HBsAg value at FU Week 36 is missing, the LOCF in conjunction with the next available observation imputation approach will be used. The available non-missing lab test closest to FU Week 36 which is no earlier/later than 12 weeks from the actual time point of interest (FU Week 24 and FU Week 48, respectively) will be imputed.

If the HBsAg value at FU Week 48 is missing, the LOCF will be used with the condition that no value earlier than FU Week 36 may be carried forward.

For all other time points, sero clearance will be analyzed as observed case without imputation.

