#### **5.4.1.3. Endpoints for Correlation**

##### **5.4.1.3.1. Association between several endpoints after the beginning of the consolidation phase**

Correlations between the following endpoints will be evaluated for participants who received at least one dose of Pegylated Interferon:

- Maximum ALT increase (U/L) vs Maximum HBV DNA increase (log10 IU/mL) between Consolidation Baseline and FU Week 4
- Maximum ALT increase (U/L) vs Maximum Neutrophils ( $10^9/L$ ) decrease between Consolidation Baseline and FU Week 4

- Maximum ALT increase (U/L) vs Maximum HBsAg decrease ( $\log_{10}$  IU/mL) between Consolidation Baseline and FU Week 4
- Additional HBsAg decline ( $\log_{10}$  IU/mL) at CW12 vs Maximum Neutrophils decrease between Consolidation Baseline and FU Week 4
- Additional HBsAg decline ( $\log_{10}$  IU/mL) at CW12 vs Maximum ALT increase (U/L) between Consolidation Baseline and FU Week 4

To evaluate the additional HBsAg decline ( $\log_{10}$  IU/mL) at CW12, a linear regression model using the four last HBsAg measures before Consolidation Baseline is performed to estimate Predicted value of HBsAg at CW12.

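### PegIFN-responder definition #2 (SAP 2.5.1) ignores the HBsAg assay floor: no one with predicted CW12 HBsAg ≤0.079 IU/mL can be a responder, and from 0.079 to 0.158 IU/mL the LLOQ/2 imputation decides

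*SAP*

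**What the plan says.** Definition #2 in SAP 2.5.1 works from a per-participant extrapolation: "A linear regression model using the four last HBsAg measures before Consolidation Baseline is performed to estimate predicted value of HBsAg at CW12". The condition for a responder is "If a decline higher than 0.5 log10 HBsAg is observed compared to the predicted value". The only eligibility requirement is at least one dose of PegIFN.

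SAP 5.1.2 says of the virology and serology data: "Those measurements collected from screening visit to the end of study will be handled according to the following rules". In Table 4 the HBsAg LLOQ is 0.05 IU/mL, and anything lower is replaced by 0.025 IU/mL, footnoted as LLOQ/2. SAP 5.3.1.1.3 has seroclearance "defined as a (quantitative) HBsAg level <LLOQ", so a participant who clears is carried at exactly 0.025.

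The classification is used in two ways:
- SAP 5.2.3 tabulates the primary endpoint "by cohort by each subgroup of interest".
- SAP 5.4.1.3.1 repeats the extrapolation, "a linear regression model using the four last HBsAg measures before Consolidation Baseline is performed to estimate Predicted value of HBsAg at CW12", to obtain an additional HBsAg decline. That variable is correlated with the largest neutrophil fall and the largest ALT rise.

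None of these sections bounds the prediction, treats results below LLOQ as censored, or provides a category for participants who cannot be classified.

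**The concern.** One side of the comparison has a floor and the other does not. Once the predicted value is low enough, the result no longer depends on what happened under PegIFN: it is fixed by the assay limit or by the imputed number.

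The primary endpoint is itself HBsAg clearance, so the rule fails in the range where a successful participant may lie. A participant who clears HBsAg can be placed outside the responder group however large the PegIFN effect was. In the 5.4.1.3.1 correlations, the same participant would enter with a small or negative additional decline.

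**Working it through.** **Inputs.** Threshold: strictly more than 0.5 log10 (SAP 2.5.1). LLOQ 0.05 IU/mL and imputed value 0.025 IU/mL (SAP Table 4). I assume the regression is on the log10 scale. The SAP does not say so, but the threshold implies it.

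**The plan's own figure.** LLOQ/2 = 0.05/2 = 0.025 IU/mL, which matches Table 4. The lowest analysable value is log10(0.025) = −1.602.

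**Lower limit.** A responder needs log10(predicted) − log10(observed) > 0.5. With the observed value at its minimum, predicted must exceed 0.025 × 10^0.5 = 0.0791 IU/mL (log10 = −1.102). The largest decline that can be recorded is:

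| Predicted CW12 (IU/mL) | Largest recordable decline (log10) | Responder possible? |
|---|---|---|
| 0.025 | 0.000 | no |
| 0.05 | 0.301 | no |
| 0.0790 | 0.4997 | no |
| 0.0791 | 0.5002 | yes |
| 0.10 | 0.602 | yes |

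Four pre-consolidation values all below LLOQ give a prediction of 0.025, so the largest recordable decline is 0.

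**Upper limit.** A result below LLOQ proves a fall of more than 0.5 log10 only if predicted is at least 0.05 × 10^0.5 = 0.158 IU/mL. Between 0.079 and 0.158, a quantifiable result (≥0.05) can never qualify and an imputed one always does. The rule there reduces to being below LLOQ at CW12. Example: predicted 0.08, true value 0.049. The true fall is log10(0.08/0.049) = 0.21; the recorded fall is log10(0.08/0.025) = 0.505, so the participant is called a responder. At 0.158 and above, the imputation cannot change the classification.

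**Example A.** HBsAg of 1.0, 0.4, 0.15 and 0.06 IU/mL at Weeks 20, 24, 28 and 32. The log10 values are 0, −0.398, −0.824 and −1.222, with mean −0.611 and slope −0.409 per 4 weeks. Week 48 (CW12) is 5.5 four-week steps beyond the midpoint: −0.611 − 5.5 × 0.409 = −2.861, or 0.0014 IU/mL. If HBsAg clears, the recorded value is −1.602, which is 1.26 log10 above prediction.

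**Example B.** HBsAg of 5, 2.5, 1.25 and 0.6 IU/mL at Weeks 24 to 36 (slope −0.306 per 4 weeks) predicts 0.073 IU/mL. The largest recordable decline is 0.466, so this participant cannot be a responder although HBsAg is still quantifiable.

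**Illustrative share.** Protocol 10.14 (Amendment 5 rationale) quotes a Week 48 HBsAg fall of 3.56 log10 (SD 1.328) in REEF-1, on 200 mg JNJ-3989 + NA in HBeAg-positive participants not currently treated. Assume a normal distribution, perfect prediction, and one baseline value for everyone:

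| Assumed baseline (IU/mL) | Mean at Week 48 (log10) | Share ≤0.079 | Share <0.158 |
|---|---|---|---|
| 10,000 | 4 − 3.56 = 0.44 | Φ((−1.102 − 0.44)/1.328) = 12% | Φ((−0.801 − 0.44)/1.328) = 17% |
| 100,000 | 5 − 3.56 = 1.44 | Φ((−1.102 − 1.44)/1.328) = 3% | Φ((−0.801 − 1.44)/1.328) = 5% |

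These shares follow from the assumed inputs and are not a forecast for this trial.

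**The case against.** The case against giving this weight is substantial:
- The study has no formal hypothesis (SAP 1.3) and no testing (SAP 5.1.1), and the subgroup table is counts and percentages.
- The Amendment 4 rationale says "there is only one patient who has met the NA treatment completion criteria and stopped NA". Since the primary endpoint requires all interventions to be stopped, about one participant could be a functional cure, apart from discretionary NA stops.
- Definition #2 never uses the word non-responder. The sentence "then the patient is considered as a “non-responder” to Pegylated Interferon" belongs to definition #1.
- Where clearance was already predicted without PegIFN, finding no extra decline reflects an assay limit and says nothing false about cure.
- Example A falls 0.41 log10 per 4 weeks. The REEF-1 average is 3.56/12 = 0.30, with slowing after Week 24.
- SAP 5.3.2.2.1 plots individual courses by functional-cure status, so a floored participant could be seen.

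Most of this stands as a limit on size. It does not remove the defect. The algebra holds for any slope, and Example B gets there at 0.31 log10 per 4 weeks. The single NA-stopper met four joint criteria, so that count does not say how many had low HBsAg. A straight line through visits that straddle the slowing may also extrapolate too low. With perhaps one possible cure, that participant's row is nearly the whole content of the table. Whether that participant lies near the floor is not known.

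**Conclusion.** The defect is real and narrow. Definition #2 cannot return responder at predicted CW12 HBsAg of 0.079 IU/mL or less, and between 0.079 and 0.158 IU/mL it returns responder for any result below LLOQ because of the imputation. The additional decline in SAP 5.4.1.3.1 inherits the same floor. The number affected is probably small and cannot be derived from the documents. The overall primary estimate is untouched.

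A reader might infer three stronger things, none of which the documents support:
- **Functional cures as a group are pushed among the non-responders, so non-responders would appear to do better.** About one possible cure cannot form such a pattern, and the non-responder label is only the implied complement in definition #2.
- **Anyone able to reach the endpoint must be near the floor at CW12.** NA may be stopped with HBsAg below 10 IU/mL (SAP 5.3.1.1.2.1), which is log10(10/0.079) = 2.1 log10 above the lower limit. A candidate for cure may therefore be fully classifiable.
- **A known share of this trial is misclassified.** The shares above depend on assumed baselines.

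The conclusion assumes a log10-scale regression. On the raw scale, Example B extrapolates to −4.2 IU/mL and the log10 comparison is undefined.

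**What to change.** In SAP 2.5.1, apply definition #2 only where predicted CW12 HBsAg is at least 0.158 IU/mL (LLOQ × 10^0.5). Show the others as a third category, 'not evaluable: prediction at assay floor', with their own seroclearance count. A cut at 0.079 would not be enough, because it keeps the band in which the imputation makes the responder. State the regression scale in the same edit.

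In SAP 5.4.1.3.1, apply the same restriction to the two correlations that use additional HBsAg decline, or treat CW12 values below LLOQ as left-censored. Mark floored participants with a distinct symbol on the scatter plots.

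This is a cheap improvement: SAP wording and one derivation flag, with no new data and no change to the primary analysis. The downside is that a few participants leave the two-way split and the two correlations.

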### 2.5.2. Subgroups for Safety Analyses

- Sex: Male, Female
- Race: Asian, non-Asian

- Body mass index (BMI) group: Underweight  $<18.5$ , Normal  $\geq 18.5$  -  $<25$ , Overweight  $\geq 25$  -  $<30$ , and Obese  $\geq 30$
- Age categories: 18 years -  $\leq 30$  years,  $>30$  years

## 2.6. Missing and Partial Dates Imputation Rules

For analysis and reporting purposes, missing or partial dates in adverse event (AE onset date; AE end date), HBV diagnosis and infection dates, concomitant therapies (start date; end date) will be imputed according to the rules in the following subsections. The original, non-imputed, dates will be used only in listings.

### 2.6.1. Adverse Event Onset Date and Resolution Date

Partial AE onset dates will be imputed as follows:

- If the AE onset date is missing the day only, it will be set to:
  - The first day of the month when the AE occurred, if month/year of the AE onset date is different than the month/year of the first administration of study treatment date in induction phase.
  - The day of the first study treatment administration in induction phase, if the month/year of the AE onset date is the same as the month/year of the first study treatment administration in induction phase but the month/year of the AE resolution date is different.
  - The earliest between the day of the first study treatment administration date in induction phase and day of AE resolution date, if month/year of the AE onset are the same as both the month/year of the first study drug administration in induction phase and the AE resolution date.
- If the AE onset date is missing both day and month, it will be set to the earliest of:
  - January 1 of the year of onset, as long as this date is on or after the first study treatment administration in induction phase.
  - Month and day of the first study treatment administration in induction phase, if this date is in the same year of AE onset date.
  - December 31 if the AE onset date year is prior to the year of the first study treatment administration in induction phase.
  - The AE resolution date.
- Completely missing onset dates will not be imputed.

Partial AE resolution dates not marked as ongoing will be imputed as follows:

- If the resolution date of an AE is missing the day only, it will be set to the earliest of the last day of that month or the day of the date of death, if the participant died in that month.
- If the resolution date of an AE is missing both day and month, it will be set to the earliest of December 31 of that year or the day and month of the date of death, if the participant died in that year.

- Completely missing resolution dates will not be imputed.

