- Per Protocol Amendment #5, participants will be randomized at baseline in a 1:1 ratio to one of the following intervention arms: JNJ-3989+JNJ-6379+NA (Cohort 2, Arm 3) or JNJ-3989+NA (Cohort 2, Arm 4). Upon completion of the 36-week induction phase, all participants will enter the 12-week consolidation phase during which they will have PegIFN- $\alpha$ 2a added to their treatment regimen.

**Note:** With the implementation of an urgent safety measure, as described in Protocol Amendment 6, participants previously enrolled had to immediately switch to the new study design. Participants had to stop JNJ-6379 treatment immediately and continue with JNJ-3989+NA treatment up to the end of the induction phase and will then enter the 12-week consolidation phase during which they will have PegIFN- $\alpha$ 2a added to their treatment regimen.

- As of Protocol Amendment 6, the study will continue as a single-arm study (JNJ-3989+NA+PegIFN- $\alpha$ 2a). All newly enrolled participants will receive JNJ-3989+NA for 36 weeks (induction phase) and will then enter the 12-week consolidation phase during which they will have PegIFN- $\alpha$ 2a added to their treatment regimen.

At the end of the consolidation phase, all participants will enter the FU phase and stop treatment with JNJ-3989+PegIFN- $\alpha$ 2a. If NA treatment completion criteria (HBsAg  $<10$  IU/mL, and HBeAg-negative, and HBV DNA  $<$ LLOQ, and ALT  $<$ 3x upper limit of normal [ULN]) have been met at consolidation Week 12, NA will also be stopped at the next scheduled visit (ie, FU Week 2), otherwise NA treatment will continue during the complete FU phase. Participants will be monitored closely during the 48-week FU phase and should restart NA treatment in accordance with the NA re-treatment criteria.

As of protocol Amendment #6, study intervention consists of:

- 200 mg JNJ-3989 (SC injection Q4W)
- 245 mg tenofovir disoproxil (tablets qd) – **Note:** tenofovir disoproxil may be supplied as fumarate or maleate
- 180 µg PegIFN- $\alpha$ 2a (SC injection, QW)

**Note:** Most participants enrolled before Protocol Amendment #6 was in effect, also received 250 mg JNJ-6379 (tablets qd) as part of their study intervention.

All participants will be considered to have completed the study if they have completed the assessments of the end-of-study (EOS) visit (ie, FU Week 48).

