## 2. GENERAL ANALYSIS DEFINITIONS

The SAP will use throughout the document the following definitions:

The term “**induction phase**” corresponds to the first treatment phase of the study starting with enrollment into induction phase of flexible duration of 36-60 weeks (inclusive) for Cohort 1 and starting with randomization or enrollment into the induction phase of a fixed duration of 36 weeks for Cohort 2.

The term “**consolidation phase**” corresponds to the second treatment phase of the study starting with the first PegIFN- $\alpha$ 2a intake with a fixed duration of 12 weeks for both cohorts.

- *Study treatment/intervention* refers to: JNJ-3989, JNJ-6379, NA (TeD, or TAF) and PegIFN- $\alpha$ 2a prior to Protocol Amendment #6; JNJ-3989, NA (TeD, or TAF) and PegIFN- $\alpha$ 2a as of Protocol Amendment #6.
- *Study agent* refers to: JNJ-3989, JNJ-6379, and PegIFN- $\alpha$ 2a prior to Protocol Amendment #6; JNJ-3989 and PegIFN- $\alpha$ 2a as of Protocol Amendment #6.

- *Study intervention arm* will be specified with Cohort 1 and Cohort 2 which are distinguished between participants enrolled prior to or after Protocol Amendment #6 as the Protocol Amendment #5 was not implemented due to the USM and no participants will be receiving Protocol Amendment #5 treatment. All participants enrolled prior to the Protocol Amendment #5 will comprise Cohort 1. The participants enrolled after approval of Amendment #6 who will comprise Cohort 2. The Study intervention arm in the SAP will be
  - Cohort 1:
    - JNJ-3989 + JNJ-6379 + NA + PegIFN- $\alpha$ 2a
    - JNJ-3989 + NA + PegIFN- $\alpha$ 2a
  - Cohort 2:
    - JNJ-3989 + NA + PegIFN- $\alpha$ 2a

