**Table 1: Analysis Phases Start and End Dates**

Analysis phase	Start date	End date
Screening	The date of signing the informed consent	1 day before the first study agent intake (excluding PegIFN- $\alpha$ 2a)
Induction phase	Cohort1: Date of first study agent intake (excluding PegIFN- $\alpha$ 2a)	Cohort1: Participants who are randomized: Min{Max[Date of first PegIFN- $\alpha$ 2a intake, Date of randomization] -1 day, cut-off date b }  Participants who are not randomized but receive PegIFN-<math>\alpha</math>2a: Min[Date of first PegIFN- $\alpha$ 2a intake-1 day, cut-off date b ]  Participants who are not randomized and did not receive PegIFN-<math>\alpha</math>2a: Min{Min[JNJ-3989 discontinuation date a , early study withdrawal visit date, max(Week 36 to 60 visit date from induction phase)] + 5 days a , cut-off date b }
	Cohort 2: Date of first study agent intake (excluding PegIFN- $\alpha$ 2a)	Cohort 2: Participants who receive PegIFN-<math>\alpha</math>2a: Min[Date of first PegIFN- $\alpha$ 2a intake – 1 day, cut-off date b ]  Participants who did not receive PegIFN-<math>\alpha</math>2a: Min{Min[JNJ-3989 discontinuation date a , early study withdrawal visit date, Week 36 visit date from induction phase] + 5 days a , cut-off date b }

Analysis phase	Start date	End date
Consolidation phase	Cohort 1: Participants who receive PegIFN- <math>\alpha</math>2a: Date of first PegIFN- $\alpha$ 2a intake  Participants who did not receive PegIFN- <math>\alpha</math>2a: date of any study agent intake after Max[Week 36 to 60 visit date]  Otherwise: Missing	Cohort1: Participants who did not withdraw from the study prior to the Consolidation Week (CW) 12 visit date: Min{Max[last intake date of any study agent (excluding NA), CW c 12], JNJ-3989 discontinuation date a } + 5 days a or cut-off date b , whichever occurs first  Participants who withdrew from the study prior to the Consolidation Week 12 visit date: Min[JNJ-3989 discontinuation date a , early study withdrawal visit date] + 5 days a or cut-off date b , whichever occurs first  Otherwise: Missing

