### 6.1.2. Analysis Methods

The adverse events will be summarized by cohort and by analysis phase. Adverse events will be allocated to phases based on their start date. If the start date of an event falls between (or on) the start and stop date of an analysis phase, the AE will be attributed to that phase (treatment-emergent principle). For imputation of partially/fully missing dates please see Section 2.6.1. In case of a completely missing start date, the event is allocated to the induction study intervention phase, except if the end date of the AE falls before the first administration of study treatment in induction phase (Induction Day 1).

An overview table will summarize the incidence of TEAEs classified in the following categories: Aes, serious Aes, related Aes, Aes leading to treatment discontinuation, and fatal Aes by presenting by the number and percentage of participants who experienced at least one of such AE. The overview Aes table will be also presented stratified by the subgroup of interests identified in Section 2.5.2.

AE relationship to study treatment is grouped into either related or not related category. A related AE is defined as with possible, probable, or very likely relationship with study treatment; not related, otherwise.

All adverse events will be presented in a descending order by incidence based on all participants (Total column). The following TEAEs tables will be included in the analysis:

- All TEAEs
- Serious TEAEs
- At least grade 3 TEAEs
- At least grade 2 TEAEs and related
- TEAEs leading to treatment discontinuation
- Related TEAEs

All serious TEAE, related TEAE, TEAE leading to death, TEAE leading to treatment or study discontinuation, TEAE of at least grade 3, or adverse events of special interest (AESIs) will be listed separately. Listings will include all information collected on the Adverse Event CRF pages (e.g. information on time of onset, duration of events, time of resolution, concomitant therapies and relationship to study treatment).

For participants reporting rash, a listing with specific grade will be provided.

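### SAP 2.6.1 checks partial AE onset dates only against the first induction dose, so day-missing events in the month PegIFN-α2a or follow-up starts can be filed under the wrong phase

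*SAP*

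**What the plan says.** SAP 2.6.1 has three branches for an onset with only the day missing. Outside the month of the first induction-phase dose, the onset becomes "The first day of the month when the AE occurred, if month/year of the AE onset date is different than the month/year of" that first administration. Within that month it becomes "The day of the first study treatment administration in induction phase, if the month/year of the AE onset date is the same as" the month of first dosing and the event resolves in a different month. If it resolves in the same month, the earlier of the dosing day and the resolution day is used. The first PegIFN-α2a dose and the start of follow-up appear in none of the branches.

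SAP 6.1.2 then states: "Adverse events will be allocated to phases based on their start date". It adds: "For imputation of partially/fully missing dates please see Section 2.6.1". SAP 2.6 says of the dates as recorded: "The original, non-imputed, dates will be used only in listings". The tables therefore run on the imputed date.

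In SAP Table 1, for participants given PegIFN-α2a, consolidation begins on the date of the first PegIFN-α2a dose and induction in general ends the day before. Follow-up begins the day after consolidation ends. SAP 6 presents safety by analysis phase and cohort, and SAP 6.1.3 does the same for AEs of special interest (AESIs).

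**The concern.** At the first induction dose, the SAP resolves an ambiguous onset in favour of treatment: an event that could have begun on drug is counted as having begun on drug. When a second active agent with its own toxicity is added, that protection is missing. An event that began the day after the first PegIFN-α2a injection, recorded with month and year only, is tabulated as an induction event.

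The phase split carries weight here. Cohort 2 is single-arm and all its participants are planned to receive PegIFN-α2a, so there is no randomised comparison without it. Protocol 2.3.3 says the effect of adding PegIFN-α2a on ALT elevations is not known, and Protocol 2.3.2.2.3 lists a possible added hematologic risk from combining it with the investigational agents. Both are AESI categories tabulated by phase. SAP 3.3.1 also schedules a data review after 10 participants have had 4 weeks of PegIFN-α2a, which is the period most exposed to the misfiling. With about 33 participants in Cohort 2, one misfiled participant moves an incidence by 1/33, about 3 percentage points.

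**Working it through.** The plan gives no figure to reproduce. The check is whether the rule does what it appears to do, and over how many days.

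**Inputs**
- Imputation rule: SAP 2.6.1.
- Phase boundaries: SAP Table 1.
- Interval from first dose to first PegIFN-α2a dose in Cohort 2: 36 weeks = 252 days. SAP 1.2: "All newly enrolled participants will receive JNJ-3989+NA for 36 weeks (induction phase) and will then enter the 12-week consolidation phase".
- Consolidation: 84 days to the Week 12 visit, so 85 days inclusive, or 90 with Table 1's 5-day extension.
- Assumption: onsets are spread evenly over days. The number of AEs lacking an onset day is not given, so results are shares of consolidation AEs with a missing day.

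**One participant**

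First dose 3 November 2021, PegIFN-α2a 13 July 2022, Consolidation Week 12 on 5 October 2022, follow-up from 6 October 2022.
- True onset 14 July, recorded as July 2022: imputed 1 July, filed under induction. True phase: consolidation.
- True onset 7 October, recorded as October 2022: imputed 1 October, filed under consolidation. True phase: follow-up.

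**All start dates**

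The rule was applied to 1,460 consecutive first-dose dates.
- The first dose and the first PegIFN-α2a dose share a calendar month in 0 of 1,460 cases, so the 1st-of-month branch always applies.
- PegIFN-α2a starts after the 1st in 1,412 of 1,460 cases (96.7%).
- Consolidation days exposed to filing under induction: mean 14.7 per participant. 14.72/85 = 17.3%; 14.72/90 = 16.4%.
- If half of consolidation AEs start in the first 4 weeks, the share lost is 26%; if 70% do, it is 37%.
- Follow-up days pulled into consolidation: also 14.7 on average.

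**Net effect on the consolidation count**

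Let r be the AE rate in consolidation divided by that in follow-up. Net change = (14.72/r - 14.72)/85, or over 90 with the extension.

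| r | 85 days | 90 days |
|---|---|---|
| 1 | about 0% | about 0% |
| 2 | -8.7% | -8.2% |
| 3 | -11.6% | -10.9% |
| 5 | -13.9% | -13.1% |

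**Year-only onsets**

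For the year in which PegIFN-α2a starts, SAP 2.6.1 gives the first-dose date or 1 January, or an earlier resolution date; this normally falls in induction. If consolidation spans a New Year, which happens for about 84/365 = 23% of start dates, year-only events of the new year are set to 1 January and land in consolidation. The direction is not uniform.

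**The case against.** The strongest objection concerns direction. A reader might infer that the rule always moves events away from PegIFN-α2a and so under-counts that phase. The documents do not support this. The follow-up boundary works the other way with the same average number of days, and a net deficit appears only if AEs are more frequent under PegIFN-α2a than in follow-up. That is plausible but assumed. The offset does not repair the tables, however. It replaces events that began on PegIFN-α2a with different events that began after treatment, so tables by preferred term and by AESI can be wrong at both ends.

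A reader might also infer that these AE tables are the only within-study view of what PegIFN-α2a adds. They are not. Laboratory toxicity, including neutrophils, platelets and ALT, is analysed by phase from the assessments themselves (SAP 6.2.1 and 6.2.2). SAP 5.4.1.3.1 relates ALT and neutrophil changes directly to the consolidation baseline.

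Three further points stand:
- Partial dates near this boundary may be rare. The end-of-induction visit is Consolidation Day 1, and AEs are reviewed there and at Consolidation Weeks 2, 4, 6, 8 and 12.
- No event disappears. Serious, related, grade 3 or higher, discontinuation-related and special-interest AEs are listed, and listings keep the recorded dates.
- The study is exploratory and its safety summaries are descriptive, so no decision rule depends on these percentages.

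These points limit the size of the problem. They do not show that the rule places the events correctly.

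**Conclusion.** The point holds as a defect of allocation at both later phase boundaries. That a day-missing event in the PegIFN-α2a start month goes to induction, unless PegIFN-α2a starts on the 1st, follows from the SAP text without any assumption.

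The size is conditional. With even onsets, 16% to 17% of consolidation AEs with a missing day are filed under induction, and more if events cluster early. After the opposite shift from follow-up, the net change is about 0 at equal rates and about -8% to -14% at rate ratios of 2 to 5. Overall treatment-emergent counts do not change. The absolute number depends on how many onset dates are partial, which is unknown and may be small.

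The documents do not support a claim of uniform anti-conservative bias, nor the inference that year-only dates always go the same way.

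**What to change.** Add one clause to SAP 2.6.1: when only the day is missing, the onset month and year equal those of the consolidation start date in Table 1, and the AE did not resolve before that date, impute the consolidation start date. This mirrors the existing first-dose convention. Do not extend it to year-only dates: on average about 165 induction days per participant fall in the year PegIFN-α2a starts, so such a rule could move many true induction events.

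Also report, by phase, the number of AEs whose allocation depends on an imputed date, including those in the month follow-up starts. That shows whether the issue matters in practice.

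The cost is one SAP rule, a small derivation change and one summary. The downside is that some true late-induction events of that month will count under PegIFN-α2a, and consolidation will still include some early follow-up events. As an upper bound, if no induction event of that month is known to have resolved before PegIFN-α2a and induction and follow-up share one AE rate, the excess among day-missing AEs is (14.7 + 14.7)/(85r): about 35% at r = 1 and 12% at r = 3. This over-counts rather than under-counts the PegIFN-α2a phase, which is the conservative direction for its safety. The gain is that events beginning on PegIFN-α2a are no longer lost to induction, not that the total becomes exact.
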